8.3. Electrocardiogram

Overall interpretation of ECG data, including normal, abnormal and clinically significant, abnormal and not clinically significant will be presented in the by-subject listings only.

8.4. Physical Examination

Physical examination results will be presented in the by-subject listings only.

8.5. Vital Signs

Mean and mean change from baseline in height, weight, and vital signs data will be summarized by visit. The hypertension status will be classified as below based on age, gender, and height-adjusted systolic or diastolic BP percentile results [Flynn 2017]. The hypertension status will be summarized by visit.

- Normal BP: BP <90th percentile for age, sex, and height; or <120/<80 mm Hg for adolescents ≥13 years old;
- Elevated BP: BP reading ≥90th percentile and <95th percentile for age, sex, and height; or 120 to 129/<80 mm Hg for adolescents ≥13 years old;
- Hypertension: BP ≥95th percentile for age, sex, and height; or ≥130/80 mm Hg for adolescents ≥13 years old.

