4.2. Inclusion Criteria

1. Signed and dated informed consent document indicating that the parent(s)/caregiver(s) of the subject has been informed of all pertinent aspects of the study prior to initiation of any study-related procedures.
2. Males ≥ 6 months to <2 years of age.
3. Body weight ≥ 7.5 kg.
4. Willingness and ability of the subject's parent(s)/caregiver(s) to comply with scheduled visits, study drug administration plan, study procedures, and study restrictions.
5. Diagnosis of DMD based on an elevated serum CK and genotypic evidence of dystrophinopathy.
6. Documentation of the presence of a nonsense mutation of the dystrophin gene as determined by gene sequencing confirmed by a PTC designee is required prior to enrollment.

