7. STUDY ASSESSMENTS AND PROCEDURES

7.1. Schedule of Events and Study Parameters

Subjects may be in the study for up to 4 weeks prior to receiving study drug at the baseline visit (Visit 2) and for 4 weeks \pm 7 days after last study drug administration (Visit 5).

The timing and types of procedures and assessments for this study are specified below in [Table 2](#).

Table 2: Schedule of Assessments

Study Period	Screening ^a	Baseline/ Start of Treatment ^b	Treatment Phase		EOT/ET ^c	Post- Treatment Follow-Up/ EOS ^d
Visit	Visit 1	Visit 2^e	Visit 3^e	Visit 4	Visit 5^e	Visit 6
Week	-	Week 0	Week 4	Week 12	Week 24	Week 28
Visit Window (days)	(-28 to -1)	0	±7	±7	±7	±7
Eligibility						
Informed Consent ^f	X					
Inclusion/Exclusion	X	X				
Medical/Surgical History	X	X				
Demographics	X					
Safety Assessments						
Physical Examination ^g	X	X	X	X	X	
Clinical Labs ^h	X	X	X	X	X	
Blood Sample for Gene Sequencing ⁱ	X					
Height/Weight/BMI	X	X	X	X	X	
Vitals (HR and BP) ^k	X	X	X	X	X	
ECG ^l	X	X	X		X	
AE/SAE Monitoring	X	X	X	X	X	X
Concomitant Medications ^m	X	X	X	X	X	X
PK Blood Sampling (VAMS) ⁿ		X	X		X	
Blood/Plasma Partition Sampling ^o		X	X		X	
Study Drug Administration						
Dispense Drug		X		X		
Unused Drug Return/Compliance			X	X ^p	X	

Abbreviations: AE, adverse event; BMI, body mass index; BP, blood pressure; CL/F, apparent clearance; C_{trough}, trough concentration (plasma concentration pre morning dose); ECG, electrocardiogram; EOS, end of study; EOT, end of treatment; ET, early termination; HR, heart rate; PK, pharmacokinetic; SAE, serious adverse event; VAMS, volumetric absorptive microsampling

^a Screening procedures must take place within 28 days of baseline (Visit 2).

^b Any screening procedure completed within and including 14 days of baseline (Visit 2) can serve as baseline assessment and does not need to be repeated at Visit 2.

^c Subjects who terminate the study early are to complete all assessments required for EOT/ET (Visit 5) prior to leaving the study and will be contacted by phone 4 weeks from the final dose of study medication for the post-treatment follow-up/EOS (Visit 6).

^d Post-treatment follow-up will be conducted by phone 4 weeks ± 7 days from last day of study treatment for review of adverse events and concomitant medications. Post-treatment follow-up is not required if subjects are transitioning to another ataluren clinical trial.

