8.5.4. Secondary Variables - PK Parameters

The PK analyses will be performed using the PK population defined above (Section 8.4). The PK parameters will be summarized and described using descriptive statistics and results placed into context with PK data from previous studies.

The following PK parameters will be derived, when appropriate and data permitting, using noncompartmental analysis methods following the morning dose at baseline (Visit 2), Week 4 (Visit 3), and EOT at Week 24 (Visit 5):

- AUC will be derived using the linear trapezoidal rule during the ascending portion of the curve and the log-trapezoidal rule during the descending portion of the curve. AUC_{0-24} after the morning dose and $AUC_{0-\tau}$ following every dose will be derived.
- C_{max}
- T_{max}
- C_{trough} (concentration prior to the morning dose)

Apparent clearance (CL/F) and $T_{1/2}$ may also be assessed, if feasible.

The PK parameters will be investigated based on frequent blood sampling. At each assessment period, blood sampling will occur at pre-dose, and 1-, 2-, 3-, and 4-hours post-dose following the morning and mid-day ataluren doses, and at pre-dose, 1-, 2-, 3-, 4-, and 12- (before the next day dose) hours after the evening ataluren dose.

Blood/plasma partitioning will be determined at 2.5 hour and 4.5 hour post morning ataluren dose at each visit.

8.5.4.1. *PK Analysis Methods*

Observed values of plasma concentrations for ataluren will be summarized at baseline (Visit 2), Week 4 (Visit 3), and EOT at Week 24 (Visit 5).

Individual PK parameters will be derived using actual sampling and dosing times. The PK parameters will be summarized with descriptive statistics at baseline (Visit 2), Week 4 (Visit 3), and EOT at Week 24 (Visit 5). (eg, n, arithmetic mean, standard deviation, standard error, median, min, and max, CV% mean, geometric mean, and CV% geometric mean). The analysis will be performed with a fully validated version of Phoenix WinNonlin V6.3 or higher.

Additional information will be provided in the PK analysis plan.

8.5.5. *Other Variables*

8.5.5.1. *Vital Signs and Physical Examination*

Vital signs (height, weight, BMI, systolic and diastolic BP, and heart rate) and physical examination data will be listed and summarized by visit and overall. Where appropriate, changes from baseline will be summarized by visit.

8.5.5.2. *Laboratory Values*

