2.4. Sample Size

Sample size is not based on any formal statistical hypothesis for this study. It is anticipated that up to 10 subjects (minimum of 6 subjects) will be enrolled.

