4. GENERAL CONSIDERATIONS

4.1. Tables, Figures, and Listings

Summary statistics for continuous variables will include n (number of subjects), mean, median, minimum, and maximum. For PK analysis, n, mean, SD, coefficient of variation (CV), geometric mean, and geometric mean CV will also be provided for PK population only. Summary statistics for categorical variables will include N (number of subjects in population), n (number of subjects in category), % (percent of subjects in category). Where applicable, the summary data will also be provided in graphical presentation.

By-subject data listings will be created for each eCRF domain sorted by treatment, subject, and associated dates, where applicable.

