5.4. Demographic and Baseline Characteristics

Demographic and baseline characteristics including age (in month), gender, race, ethnicity, height, weight, and BMI will be summarized for safety population.

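### Raw mean change in height and weight cannot show slowed growth in boys aged 6 to under 24 months; SAP 8.5 should add age- and sex-standardised z-scores

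*SAP*

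**What the plan says.** Protocol Table 2 places "Height/Weight/BMI" among the safety assessments at all five on-site visits. On analysis, the two documents say:

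- **Protocol 8.5.5.1:** "Vital signs (height, weight, BMI, systolic and diastolic BP, and heart rate) and physical examination data will be listed and summarized by visit and overall". Changes from baseline are added by visit where appropriate.
- **SAP 8.5:** "Mean and mean change from baseline in height, weight, and vital signs data will be summarized by visit". BMI is not named here. In SAP 5.4 it appears only among the baseline characteristics.
- **SAP 8.5, on blood pressure:** "The hypertension status will be classified as below based on age, gender, and height-adjusted systolic or diastolic BP percentile results".
- **SAP 4.1:** "By-subject data listings will be created for each eCRF domain sorted by treatment, subject, and associated dates, where applicable". Summaries of continuous variables give n, mean, median, minimum and maximum.
- **SAP 4.5:** analyses use the nominal visits on the eCRF.

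Neither document mentions a z-score, percentile, velocity or reference standard for height, weight or BMI. The table, figure and listing shells are in a separate document (SAP 11) that was not available.

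The entry criterion is "Males ≥ 6 months to <2 years of age" (protocol 4.2). On numbers, SAP 2.4 says: "It is anticipated that up to 10 subjects (minimum of 6 subjects) will be enrolled". Ataluren is the only study treatment, so there is no comparator.

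**The concern.** A raw change in kilograms or centimetres means something only against the change expected over the same period. A control arm or a growth standard would supply that expectation, and this plan has neither. Expected gain also depends on age. Pooling a child who enters at 6 months with one who enters at 23 months therefore gives a mean that moves with the age mix as well as with growth.

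The primary objective is safety and tolerability in very young children. Protocol 1.3.1 lists nausea and vomiting among the possibly related events in children aged 2 to under 5 years, and protocol 5.4.1 discourages corticosteroids but permits them. A table of positive mean gains could be read as reassurance about growth that it does not provide.

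**Working it through.** The plan states no growth effect, and its sample size rests on no hypothesis, so there is no figure to reproduce. All growth figures below are assumptions made for illustration. Only the visit windows in step 3 come from the documents.

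**1. Does the sign of the mean change separate normal from slowed growth?**

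Assumed normal 24-week gain: weight 1.0 to 2.0 kg (SD of the gain 0.4 to 0.7 kg); length 4 to 8 cm (SD 1 to 2 cm). With mean gain m, SD s and n children, P(mean change > 0) = Φ(m / (s/√n)). The SD is held fixed when growth is halved. The least favourable combinations are:

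| Measure | n | Normal gain | SD | Halved gain | P(mean change > 0) |
|---|---|---|---|---|---|
| Weight | 6 | 1.0 kg | 0.7 kg | 0.5 kg | 96.0% |
| Weight | 10 | 1.0 kg | 0.7 kg | 0.5 kg | 98.8% |
| Length | 6 | 4 cm | 2 cm | 2 cm | 99.3% |
| Length | 10 | 4 cm | 2 cm | 2 cm | 99.9% |

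First row: 0.5 / (0.7/√6) = 1.75, and Φ(1.75) = 0.960. Every other combination in the assumed ranges gives a higher probability at the same n. With normal growth the probability is at least 99.9% throughout. A positive mean change therefore does not tell normal growth from halved growth.

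**2. Does the size of the mean change help?**

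Not without a reference. Suppose the two ends of the assumed weight range belonged to the youngest and oldest entrants. A group of the youngest at half growth (2.0/2 = +1.0 kg) would then show the same mean as a group of the oldest growing normally (+1.0 kg).

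The z-scale shows what is hidden. Near the youngest entry age only, assume a normal gain g of 1.4 to 2.0 kg and a between-child SD of weight at a given age of 0.9 to 1.1 kg, constant over the interval. This is a different SD from the SD of the gain in step 1.

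- Half growth: raw change g/2 = +0.7 to +1.0 kg. The fall in z is (g/2)/SD, from 0.7/1.1 = 0.64 to 1.0/0.9 = 1.11.
- A fall of one full z unit: raw change g − SD, from 1.4 − 1.1 = +0.3 kg to 2.0 − 0.9 = +1.1 kg.

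**3. How even is the measurement interval?**

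A screening value up to 14 days before Visit 2 may serve as baseline, and Visit 5 falls at 168 ± 7 days. The interval for a completer therefore runs from 168 − 7 = 161 days to 168 + 7 + 14 = 189 days. The spread is 28 days, and 28/168 = 17% of the treatment period. Nominal visits ignore it.

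**4. What would z-scores gain?**

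The expected change becomes zero, and slowing appears as a negative value. Assume an SD of 0.4 to 0.8 for the 24-week change in z. The 95% interval half-width is t(0.975, n−1) × s/√n, and the chance that the interval lies wholly below zero comes from the noncentral t. No interval is planned in the SAP; it serves here only as a measure of precision.

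| n | SD of change in z | Half-width | True fall 0.25 | True fall 0.5 | True fall 1.0 |
|---|---|---|---|---|---|
| 6 | 0.4 | 0.42 | 24% | 69% | >99% |
| 6 | 0.8 | 0.84 | 9% | 24% | 69% |
| 10 | 0.4 | 0.29 | 42% | 94% | >99% |
| 10 | 0.8 | 0.57 | 14% | 42% | 94% |

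Only large slowing would be reliably visible at the group level.

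**The case against.** The strongest reply is that one summary line is not the whole plan.

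- **Listings and extremes.** With 6 to 10 boys, by-subject listings are a natural way to read growth, and the planned minimum would show a child who lost weight or hardly gained. This stands, and it defeats an inference that a reader might draw, namely that the trial itself cannot detect slowed growth. The documents do not support that: the data are collected and listed. But a listing of raw values still leaves the reader to standardise each one, and a minimum change is not judged against age.
- **Other routes.** A full physical examination takes place at each on-site visit, weight is reviewed at Week 12 for dosing, and findings that need intervention or further investigation are adverse events (protocol 7.6.1). So it would be wrong to say that feeding problems or growth failure could not surface. A gradual drift across percentiles, however, need not meet that adverse-event threshold.
- **Growth is not a named endpoint or risk.** This is correct. The primary endpoint is the profile of treatment-emergent adverse events, and protocol 1.3.1 does not list growth among the risks. It does list hypertension with concomitant corticosteroids, which is a reason to standardise blood pressure. The blood pressure rule shows that the approach is familiar and practical; it does not make SAP 8.5 contradictory.
- **Assumed figures and limited gain.** Both points stand. The kilogram-to-z illustration covers the youngest entrants only. Z-scores in a small uncontrolled group cannot separate drug from disease or corticosteroids.
- **Unseen shells.** Per-child displays may already be specified there.

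**Conclusion.** The concern holds for the planned summary. Raw mean and mean change in height and weight cannot show slowed growth in this age group, because the change is positive either way and no comparator or reference is given. That step needs only ordinary growth at this age and the absence of a reference. The size rests on assumption: under the ranges in the working, a positive mean change remains at least 96% likely for weight and 99% likely for length when growth is halved. The uneven interval of 161 to 189 days is the one numerical result that follows from the documents alone.

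The conclusion does not extend to the trial's data, from which z-scores can be derived at any time, so nothing is irretrievably lost. Nor would the change turn growth into a tested outcome. This is a worthwhile, low-cost improvement to a descriptive safety table.

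**What to change.** In SAP 8.5:

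1. Convert weight, length/height and BMI at each visit to age- and sex-specific z-scores from one named growth standard, using exact age on the actual measurement date and not the nominal visit.
2. Summarise the z-score and its change from baseline by visit, and list or plot both for each child. Keep the raw values. Naming BMI here also brings the section into line with protocol 8.5.5.1.
3. Include the SD in these summaries. Protocol 8.1 lists it for continuous variables, but SAP 4.1 gives it only for the PK analysis.
4. State that the growth summary is descriptive. With 6 to 10 children, no control arm and corticosteroids discouraged but permitted, only large slowing would be reliably visible, and it could not be attributed to ataluren rather than to disease or corticosteroids.

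The cost is SAP wording, minor programming and the choice of a reference standard. SAP 5.4 shows that the inputs are already recorded: "Demographic and baseline characteristics including age (in month), gender, race, ethnicity, height, weight, and BMI will be summarized for safety population". Height and weight are also measured at each on-site visit, so no child needs a further visit or procedure.

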9. CHANGES FROM THE PROTOCOL

No changes are made to the planned analyses from the study protocol.

10. **BIBLIOGRAPHY**

Flynn, JT and Falkner, BE. New Clinical Practice Guideline for the Management of High Blood Pressure in Children and Adolescents. Hypertension 2017;70(4):683-686.

11. TABLE OF CONTENTS FOR TABLES, FIGURES, AND LISTINGS

The tables, listings, and graphs shells for the study will be provided in a separate document.

Study Period	Screening ^a	Baseline/ Start of Treatment ^b	Treatment Phase		EOT/ET°	Post- Treatment Follow- Up/ EOS ^d
Visit	Visit 1	Visit 2 ^e	Visit 3 ^e	Visit 4	Visit 5 ^e	Visit 6
Week	-	Week 0	Week 4	Week 12	Week 24	Week 28
Visit Window (days)	(-28 to -1)	0	±7	±7	±7	±7
Eligibility						
Informed Consent ^f	Х					
Inclusion/Exclusion	Х	Х				
Medical/Surgical	X	Х				
History	V					
Sefety Accessments	×					
Dhysical Examination	V	V	V	V	V	
	A V	 	^	^	^	
	X	X	X	X	X	
Blood Sample for	X					
Height/Weight/BMI	X	X	X	X	X	
Vitals (HR and BP) ^k	Х	Х	Х	Х	Х	
ECG ⁱ	Х	Х	Х		Х	
AE/SAE Monitoring	Х	Х	Х	Х	Х	Х
Concomitant Medications ^m	х	X	X	X	X	X
PK Blood Sampling (VAMS) ⁿ		Х	Х		Х	
Blood/Plasma Partition Sampling ^o		Х	Х		Х	
Study Drug						
Administration						
Dispense Drug		Х		Х		
Unused Drug Return/Compliance			X	Xp	X	

APPENDIX 1. SCHEDULE OF ASSESSMENTS

Abbreviations: AE, adverse event; BMI, body mass index; BP, blood pressure; CL/F, apparent clearance; C_{trough}, trough concentration (plasma concentration pre morning dose); ECG, electrocardiogram; EOS, end of study; EOT, end of treatment; ET, early termination; HR, heart rate; PK, pharmacokinetic; SAE, serious adverse event; VAMS, volumetric absorptive microsampling

^a Screening procedures must take place within 28 days of baseline (Visit 2).

^b Any screening procedure completed within and including 14 days of baseline (Visit 2) can serve as baseline assessment and does not need to be repeated at Visit 2.

^c Subjects who terminate the study early are to complete all assessments required for EOT/ET (Visit 5) prior to leaving the study and will be contacted by phone 4 weeks from the final dose of study medication for the post-treatment follow-up/EOS (Visit 6).

^d Post-treatment follow-up will be conducted by phone 4 weeks ± 7 days from last day of study treatment for review of adverse events and concomitant medications. Post-treatment follow-up is not required if subjects are transitioning to another ataluren clinical trial.

^e Visits 2, 3, and 5 will be conducted over the course of 24 hours due to the timing of the collection of PK samples and will require an overnight stay.

^f A signed and dated informed consent must be obtained before conducting any study procedures. Remote informed consent is permitted consistent with local policies and procedures.

⁹ A full physical examination will include evaluation of the cardiovascular system, chest and lungs, thyroid, abdomen, nervous system, skin and mucosae, musculoskeletal system, eyes, ears, nose, mouth, throat, spine, lymph nodes, and extremities.

^h Blood and urine collection will be obtained locally and submitted to the local or central laboratory for analysis. Use of standard of care labs is permitted when samples were obtained within the visit window. Clinical labs will include hematology, biochemistry, and urinalysis parameters as follows: Hematology laboratory assessments will include white blood cell count with differential, hemoglobin, hematocrit, other red cell parameters, and platelet count. Biochemistry laboratory assessments will include sodium, potassium, chloride, bicarbonate, blood urea nitrogen, creatinine, magnesium, calcium, phosphorus, uric acid, glucose, total protein, albumin, bilirubin (total, direct, and indirect), aspartate aminotransferase, alanine aminotransferase, gamma-glutamyl transferase, creatinine kinase, lactate dehydrogenase, alkaline phosphatase, total cholesterol, high density lipoprotein, low density lipoprotein, triglycerides, and cystatin C. Urinalysis assessments will include analysis for pH, specific gravity, glucose, ketones, blood, protein, urobilinogen, bilirubin, nitrite, urine protein: urine creatinine ratio (spot), and leukocyte esterase.

¹ This is to ensure a blood sample has been drawn for sequencing of the dystrophin gene. The sample will be sent to a central laboratory for analysis.

^j Weight-based dose adjustment will be assessed at Week 12.

^k Heart rate and BP determinations will be performed with the subject in a supine position after a 5-minute rest.

¹ ECGs will be read locally at investigational sites and interpreted for clinical significance.

^m Concomitant medication information will need to be collected starting 28 days prior to the first dose of study drug (Screening, Visit 1).

ⁿ PK samples (VAMS method) will be drawn at baseline (Visit 2), Week 4 (Visit 3), and Week 24 (EOT/ET) for evaluation. Samples will be drawn immediately pre-dose, and at 1-, 2-, 3-, and 4-hours post-dose following both the morning and mid-day doses and immediately pre-dose and at 1-, 2-, 3-, 4-, and 12- (before the next day morning dose) hours post-dose following the evening dose.

Blood sampling via venous draw will be conducted at Visits 2, 3, and 5. These additional samples will be taken at 2.5 -hours and 4.5 -hours post morning dose (1.5 ml each timepoint). Out of the 1.5 mL blood sample collected, at the 2.5 hour and 4.5 hour timepoints, 1 mL blood sample will be processed to plasma and the remaining 0.5 mL blood will be processed to dried blood sample using a VAMS device.

^p Parent(s)/caregiver(s) will record daily dose administration on a Study Drug Administration Record (dosing sheet) and Subjects are required to return any unused study drug.
